4.7.3 Additional safety assessments

4.7.3.1 *Laboratory variables, vital signs and electrocardiograms (ECGs)*

Not applicable

4.8 OTHER ANALYSES

4.8.1 Assessment of impact of COVID-19 pandemic

In order to assess an impact of Coronavirus Disease 2019 (COVID-19) pandemic on study conduct, the number (%) of subjects in the following categories will be also summarized on enrolled subjects:

- Subjects with a CRF
- Subjects impacted by COVID-19 pandemic situation
- Subjects with at least one major/critical protocol deviation due to COVID-19 pandemic situation, and each detailed deviation
- Subjects who discontinued the trial with following reasons of early termination due to COVID-19
 - Adverse event
 - Protocol deviation
 - Lost to follow-up
 - Withdrawal by subjects
 - Withdrawal by parent/guardian
- Visit disposition at each visit
 - COVID-19 Visit not done

- COVID-19 Visit partially done: blood sampling not performed, vaccination not performed, and no solicited safety data available
- COVID-19 At least one procedure out of time window: blood sampling out of time window, vaccination out of time window, and visit date out of time window
- COVID-19 No procedure done on site
- COVID-19 At least one procedure done by phone
- COVID-19 At least one procedure done at home

4.9 INTERIM ANALYSES

No interim/preliminary analyses are planned.

5 SUPPORTING DOCUMENTATION

5.1 APPENDIX 1 LIST OF ABBREVIATIONS

AE:	adverse event
AR:	adverse reaction
CI:	confidence interval
COVID-19:	Coronavirus Disease 2019
CRB:	case report book [all the case report forms for a subject]
CRF:	case report form
CSR:	clinical study report
D:	day
FAS:	Full Analysis Set
GM:	geometric mean
GMT:	geometric mean titer
hSBA:	serum bactericidal assay using human complement
IMP:	investigational medicinal product
LLOQ:	lower limit of quantitation
LLT:	lower-level term
MD:	missing data
MedDRA:	Medical Disctionary for Regulatory Activities
NM:	non-measurable, too large to measure
NSAID:	non-steroidal anti-inflammatory drug
PMDA:	Pharmaceuticals and Medical Device Agency
PPAS:	Per-Protocol Analysis Set
PT:	preferred term
Q1:	first quartile
Q3:	third quartile
RCDC:	reverse cumulative distribution curve
rSBA:	serum bactericidal assay using baby rabbit complement
SAE:	serious adverse event
SafAS:	Safety Analysis Set
SAP:	statistical analysis plan
SD:	standard deviation
SOC:	system organ class
ULOQ:	upper limit of quantitation
WHO-DD:	World Health Organization-drug dictionary

5.2 APPENDIX 2 CHANGES TO PROTOCOL-PLANNED ANALYSES

This section summarizes major statistical changes in the protocol amendment(s).

Table 7 - Major statistical changes in protocol amendment(s)

Amendment Number	Approval Date	Changes	Rationale
1	10-Mar-2020	No changes in protocol amendment	

5.3 APPENDIX 3 DEMOGRAPHICS AND BASELINE CHARACTERISTICS, PRIOR OR CONCOMITANT MEDICATIONS

Demographics, medical history

The following demographics and baseline characteristics, and medical history will be summarized using descriptive statistics in the randomized subjects. The demographics and baseline characteristics will also be summarized in the FAS, PPAS, and SafAS.

Demographic and baseline characteristics

- age in years as quantitative variable and in categories (2 to 9 [children], 10 to 17 [adolescents], and ≥ 18 [adults])
- gender (Male, Female)
- race (White, Asian, Black, American Indian or Alaska Native, Native Hawaiian or other Pacific Islander, Multiple, Not reported, and Unknown)
- ethnicity (Hispanic or Latino, Not Hispanic or Latino, Not Reported, and Unknown)

Medical history includes conditions/illnesses for which the subject is or has been followed by a physician or condition/illnesses that could resume during the course of the study or lead to an SAE or to a repetitive outpatient care will be collected in the CRB. Medical history will not be coded using the MedDRA.

Concomitant medications

All medications will be coded using the World Health Organization-Drug Dictionary (WHO-DD) using the version currently in effect at Sanofi at the time of database lock.

Documentation in the CRB of ongoing concomitant medication(s) will be limited to specific categories of medication(s) of interest beginning on the day of vaccination. This may include medications of interest that were started prior to the day of vaccination.

Reportable medications will be collected in the CRB from the day of vaccination to the end of the study (D30 [+14 days]).

Reportable medications include medications that impact or may impact the consistency of the safety information collected after vaccination and/or the response to vaccination. Three standard categories of reportable medications are defined:

- Category 1: antipyretics, analgesics, non-steroidal anti-inflammatory drugs (NSAIDs), corticosteroids, and other immune modulators.
 - Note: inhaled and topical steroids should not be captured.
- Category 2: Reportable medications used to define the Per-Protocol Analysis Set (PPAS). For example:
 - Influenza and other non-study vaccines: Influenza vaccine in the 2 weeks preceding the study vaccination up to the subject's termination from the study and any other vaccines (other than the study vaccine) in the 4 weeks preceding the study vaccination up to the subject's termination from the study
 - Immune globulins, blood or blood-derived products: used in the 3 months preceding the first blood draw and up to the last blood draw
 - Immunosuppressive therapy such as anti-cancer chemotherapy or radiation therapy: used in the 6 months preceding the study vaccination and the 4 weeks following the study vaccination
- Category 3: Oral or injectable antibiotics, which may interfere with bioassays used for antibody testing when taken before a blood draw.

Protocol-prohibited therapy, medication or vaccines

In general, the “prohibited” variable is not derived. All concomitant medications are reviewed by the clinical team and the value of “prohibited” variable is determined before database lock by the clinical team according to the following rule:

Only two categories of reportable medications will be considered as prohibited therapy, medication or vaccine

Category 2:

- Flu vaccines administered within 14 days pre or post each trial vaccination, including the day of the study visit vaccination
- Other vaccines not included as study vaccines, it means non-study vaccines (e.g. Oral poliovirus, Yellow fever, Japanese encephalitis, or other routine/not-routine vaccine not-described in the protocol) within the 28 days (4 weeks) preceding or after the trial vaccination, including the day of the study visit vaccination
- Immune globulins, blood or blood-derived products and Immunosuppressive therapy, as described in the protocol

Category 3:

- Antibiotics that the subject received within the 3 days preceding each Visit for blood draw related to investigational medicinal product (IMP) assessment (meningococcal vaccines)

If the above protocol-prohibited therapy, medication or vaccines are received at specific visits, it will impact the corresponding immunogenicity analyses.

The reportable medications will be summarized for the enrolled subjects. The summary will be presented based on the use of any medication and each category, and the medication considered by the sponsor as the protocol-prohibited treatment will also be summarized.

5.4 APPENDIX 4 DATA HANDLING CONVENTIONS

5.4.1 General conventions

Subject duration

The duration of a subject in the study is computed as follows:

Maximum (date of last visit, date of termination form) – (date of Visit 1) + 1.

Duration of the Study

The duration of the study (until last visit) is computed as follows:

Maximum of all subjects (date of last visit, date of termination form)
– minimum for all subjects (date Visit 1) + 1.

5.4.2 Data handling conventions for safety variables

5.4.2.1 *Solicited Reactions*

Daily intensity

All daily records for solicited reactions will be derived into daily intensity according to the following classification: None, Grade 1, Grade 2, Grade 3, or Missing. The category of Unknown will be considered Missing if Unknown is recorded.

For the derivation of daily intensities, the following sequential steps will be applied:

1. Solicited reactions (except Fever/Pyrexia) with an investigator presence recorded as “No” and with all daily records missing then all daily intensities will be derived as None.
2. For a temperature partially missing after decimal point, the data will be analyzed replacing “MD” (missing data) by zero. For example, a “39.MD” daily temperature will be considered as “39.0°C” at the time of analysis.
3. For non-measurable (NM) solicited reactions, daily intensities will correspond to daily records reported in the clinical database. For measurable solicited reactions the daily measurements reported in the clinical database will be converted based upon the intensity scales defined in the protocol; this assumes a reaction that is too large to measure (NM) is Grade 3. Note the intensity could be considered “None” (not reaction) in the analysis despite being considered a reaction by the investigator (e.g., swelling measurement > 0 mm but < 25 mm in adults).

Note: The maximum intensity on the ongoing period is derived from the record of the maximum intensity/measurement after the end of the solicited period following the rule described above in “Daily intensity”.

Maximum overall intensity

Maximum overall intensity is derived from the daily intensities computed as described above in “Daily intensity” and is calculated as the maximum of the daily intensities over the period considered.

Presence

Presence is derived from the maximum overall intensity on the period considered:

- None : No presence
- Grade 1, Grade 2, or Grade 3 : Presence
- Missing : Missing presence

Subjects with at least one non-missing presence for a specific endpoint will be included in the analysis. Conversely, those without a non-missing presence will not be included in the analysis of the endpoint.

Time of onset

Time of onset is derived from the daily intensities computed as described above in “Daily intensity”. It corresponds to the first day with intensity of Grade 1, Grade 2, or Grade 3.

Note: If a reaction is not continuous (i.e., reaction occurs over two separate periods of time intervened by at least one daily intensity Missing or None) then the time of onset is the first day of the first occurrence.

Number of days of occurrence

Number of days of occurrence over the period considered is derived from the daily intensities computed as described above in “Daily intensity”. It corresponds to the number of days with daily intensities of Grade 1, Grade 2, or Grade 3. Number of days of occurrence on the solicited period with a specified intensity may also be derived.

Overall number of days of occurrence

If a reaction is ongoing at the end of the solicited period, then the overall number of days of occurrence is derived from the daily intensities and the stop date of the reaction after the end of the solicited period. The overall number of days of occurrence is:

(stop date – last vaccination date)

+ (number of days of occurrence within the solicited period)

– length of the solicited period + 1

If the stop date is missing or incomplete (contains MD), the overall number of days of occurrence will be considered as Missing.

Ongoing

Ongoing is derived from the last daily intensity of the solicited period computed as described above in “Daily intensity” and the maximum intensity on the ongoing period. The investigator’s ongoing flag is not used because the measurement would determine the ongoing status of the reaction.

If the last daily intensity of the solicited period is at least Grade 1 and maximum intensity on the ongoing period is also at least Grade 1, then the reaction is considered ongoing. In any other cases the reaction will not be considered as ongoing.

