5.4.4 Missing data

5.4.4.1 Safety

No replacement will be done. In all subject listings, partial and missing data will be clearly indicated as missing.

Immediate

For unsolicited non-serious systemic AEs, a missing response to the “Immediate” field is assumed to have occurred after the 30-minute surveillance period and will not be imputed.

For SAEs, missing or partially missing elapsed time from last vaccination recorded if within 24 hours will be assumed to have occurred after the 30-minute surveillance period and will not be imputed. Such SAEs will not be considered as immediate.

Causality

Missing causality (relationship) for unsolicited non-serious AEs and SAEs will be considered at the time of analysis as related to vaccination.

Measurements

Partially missing temperatures will be handled as described in “Daily intensity” of [Section 5.4.2.1](#).

Intensity

For solicited reactions, missing intensities will be handled as described in “Daily intensity” of [Section 5.4.2.1](#). For unsolicited non-serious AEs, missing intensities will remain missing and will not be imputed.

Start Date and Stop Date

Missing or partially missing start dates for unsolicited AEs will remain missing and not be imputed. If the start date is missing or partially missing, the time of onset will be considered to be missing. Nevertheless, unsolicited AEs with missing time of onset will be included in analyses according to the visit collected.

Missing or partially missing stop dates for AEs (solicited reactions and unsolicited AEs) will remain missing and not be imputed.

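### For solicited reactions with no daily records, SAP 5.4.2.1 accepts an Investigator 'No' but has no rule for a 'Yes', which lowers the any-grade rate for reactions where 'Yes' implies at least Grade 1

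*SAP*

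**What the plan says.** SAP 5.4.2.1 (Solicited Reactions) builds every solicited-reaction result from daily intensities.

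- **Step 1 of the daily-intensity derivation** is the only step that uses the Investigator's presence answer, and only a 'No' triggers it. For that answer the rule reads, in part: "with all daily records missing then all daily intensities will be derived as None". Such a subject is analysed as having no reaction. Fever is excepted.
- **No step covers 'Yes'.** Steps 2 and 3 deal with incomplete temperatures and with converting records to grades.
- **Maximum.** The overall intensity "is calculated as the maximum of the daily intensities over the period considered". The SAP does not say how a Missing day enters that maximum.
- **Presence.** "Presence is derived from the maximum overall intensity on the period considered", and a missing maximum maps to "Missing : Missing presence".
- **Consequence.** "Conversely, those without a non-missing presence will not be included in the analysis of the endpoint".

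SAP 5.4.4.1 (Safety, under Missing data) adds nothing: "For solicited reactions, missing intensities will be handled as described in" the daily-intensity text of 5.4.2.1. It also says, as does Protocol 12.3.1, that safety data are not replaced.

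**The concern.** Two subjects can hand in equally empty records and be treated differently according to the Investigator's answer. The 'No' is believed and the subject enters the denominator. The 'Yes' is ignored and the subject disappears. Non-reactors with blank records are kept and reactors with blank records are removed, so where 'Yes' implies at least Grade 1 the reported rate is pulled down.

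Occurrence of solicited injection site and systemic reactions is a secondary safety endpoint (Protocol 9.2.2.2; SAP Table 2). The SAP is more inclusive elsewhere. Under 5.4.2.2 and 5.4.4.1 an unsolicited event with a verbatim term still counts when its intensity is missing, and missing causality is taken as related.

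**Working it through.** The documents state no figure on this point, so there is none to reproduce.

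**Step 1. Apply the written rules to a non-fever reaction.**

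| Investigator answer | Daily records | Result under SAP 5.4.2.1 |
|---|---|---|
| No | all missing | no presence; in the denominator |
| Yes | all missing | Missing presence; out of numerator and denominator |
| Yes | at least one day of Grade 1 to 3, with Missing days ignored in the maximum | presence; nothing lost |
| Yes | some days None, rest missing | not determined: no presence if Missing days are ignored, excluded if the maximum is taken as Missing |

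Fever with all records missing is excluded whatever the answer, so the asymmetry does not arise there.

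**Step 2. Where does 'Yes' imply at least Grade 1?** The grading scales in Protocol Tables 1 to 3 settle this.

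- Pain, headache, malaise and myalgia: Grade 1 is the mildest form of the reaction, at all ages.
- Erythema, swelling and induration at 2 to 9 years: any size above 0 mm is Grade 1 (Table 1).
- The same three at 10 years and over: Grade 1 starts at 25 mm (Table 2). SAP 5.4.2.1 step 3 accepts that a smaller reaction reported by the Investigator is analysed as None. Here 'Yes' does not imply Grade 1.

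**Step 3. Direction for the first two groups.** Let R be the true reactors among n subjects, and m the reactors with 'Yes' and blank records. The reported rate is (R − m)/(n − m). It is below R/n when n(R − m) < R(n − m), that is when Rm < nm, which holds whenever m > 0 and R < n.

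**Step 4. Illustration.** n = 180 per group comes from SAP section 2. R and m are assumptions, since the documents give neither. All 180 are taken to be in the safety set, and the Investigator's answers are taken as true.

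| True rate | m = 1 | m = 5 | m = 9 |
|---|---|---|---|
| 18/180 = 10.0% | 17/179 = 9.5% | 13/175 = 7.4% | 9/171 = 5.3% |
| 72/180 = 40.0% | 71/179 = 39.7% | 67/175 = 38.3% | 63/171 = 36.8% |
| 108/180 = 60.0% | 107/179 = 59.8% | 103/175 = 58.9% | 99/171 = 57.9% |

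**Step 5. Would dropping both answers be better?** Take 72 true reactors in 180.

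- 5 'Yes' and 5 'No' blank records: the SAP gives 67/175 = 38.3%; excluding both kinds gives 67/170 = 39.4%; using both answers gives 72/180 = 40.0%.
- 2 'Yes' and 8 'No': the SAP gives 70/178 = 39.3%; excluding both gives 70/170 = 41.2%; using both gives 40.0%.

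Only using both answers returns the true rate in each case.

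**The case against.** **Data collection already targets these records.** The diary is reviewed at Visit 2 (Protocol 5.1.4), missing or discrepant entries are clarified verbally (13.2), consistency checks raise queries (11.2), and a blind data review precedes lock (11.3). This stands as a reason to expect few cases. It supplies no analysis rule for those that remain, and someone who recalls a reaction weeks later may not be able to restore daily grades.

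**Deriving results from recorded intensity is deliberate.** The SAP also sets aside the Investigator's ongoing flag in favour of the measurement. That is sound where a measurement exists. With blank records there is none, and step 1 already relies on the Investigator when the answer is 'No'. The no-replacement principle does not help either, because step 1 itself replaces blanks with None.

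**The bias is not downward everywhere.** A reader might infer that the rule can only lower any solicited-reaction rate. For erythema, swelling and induration at 10 years and over this fails. A 'Yes' may be a reaction under 25 mm, which is a non-reaction by the protocol's scale, and dropping such subjects raises the rate: 20/180 = 11.1% becomes 20/175 = 11.4% if five are dropped. This objection stands, and the point is limited accordingly.

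**A partly filled card is not shown to be counted as no reaction.** A reader might infer that 'Yes' with recorded days of None is analysed as no reaction. That requires Missing days to be ignored in the maximum, which the SAP does not state. It also requires every reaction day to be blank. In the earlier adolescent and adult trial against the same comparator (Protocol 1.2.2.2), most reactions began between D0 and D3 and most lasted 1 to 3 days.

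**The effect is small beside sampling error.** At 40% with n = 180, the half-width of an approximate 95% interval is 1.96 × √(0.4 × 0.6/180) = 7.2 points, against a shift of 1.7 points with five lost reactors. This is true, but a systematic shift that is cheap to remove need not be accepted.

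**Conclusion.** The concern holds in a limited form. SAP 5.4.2.1 retains the non-reactor with blank records and drops the documented reactor. For pain, headache, malaise and myalgia at all ages, and for erythema, swelling and induration at 2 to 9 years, this can only lower the any-grade rate, provided the Investigator's 'Yes' is correct.

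The size cannot be found from the documents. In the 40% illustration it runs from −0.3 points (one lost reactor) to −3.2 points (nine). Given diary review and queries, the real shift is probably towards the small end.

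Only descriptive secondary safety rates are affected; SAP 4.7 plans no safety testing, and the primary non-inferiority analysis is untouched. A reader might infer that the rule favours one vaccine. The documents do not support that: the same rule applies to both groups, and the comparison is biased only if missingness differs by arm.

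**What to change.** Amend SAP 5.4.2.1 as follows.

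1. For pain, headache, malaise and myalgia at all ages, and for erythema, swelling and induration at 2 to 9 years: Investigator presence 'Yes' with all daily records missing gives Presence = Yes with intensity Missing. The subject counts in numerator and denominator of the any-grade tables and appears in a missing-intensity row of the intensity tables.
2. State how Missing days enter the maximum. For the same reactions, treat 'Yes' with some days missing and all recorded days None as in item 1.
3. Keep fever excepted; it is defined by temperature.
4. For erythema, swelling and induration at 10 years and over, leave the rule unchanged. Report by group the number of 'Yes' answers with no graded day, and a sensitivity rate that counts them as present.

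The limits in items 1, 3 and 4 are needed. A general rule that 'Yes' plus any missing day means present would turn an adult with 15 mm swelling recorded on seven days and one blank day into a reactor, against Protocol Table 2.

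The cost is a short SAP addition and minor programming. The downside is that a few reactions enter the any-grade rate without a grade. Their onset and number of days, which the SAP derives from daily intensities, would be missing too.

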5.4.2.2 Unsolicited Non-serious AEs

Presence

An observation will be considered an event if it has at least a verbatim term and is not a Grade 0 intensity event. Grade 0 events should be included in the listing “Unsolicited non-serious adverse events not included in the safety analysis.”

Intensity

Intensity for unsolicited non-serious AE will be derived according to the following classification: None: Grade 1, Grade 2, Grade 3, or Missing. The category of Unknown will be considered Missing if Unknown is recorded as well as the intensity classification of solicited reactions.

If the unsolicited non-serious AE is measurable and its preferred term is part of the list of solicited reactions, then the measurement is derived based upon and following the same rule than the intensity scales defined in the protocol for that measurable injection site or systemic reaction.

Intensity for the other unsolicited non-serious AEs will correspond to the value reported in the CRF.

The maximum intensity corresponds to the highest intensity for a unique term.

Last vaccination

Last vaccination before any unsolicited non-serious AE is the study vaccination at Visit 1.

Time of onset

Time of onset is derived from the start date of the unsolicited non-serious AE provided in the clinical database and the date of last vaccination:

start date of the unsolicited non-serious AEs – date of previous vaccination

The time of onset should be considered as missing only if one or both of the dates are missing or partially missing.

The unsolicited non-serious AEs will be analyzed “Within 30 days”, which corresponds to AEs with a time of onset between 0 and 30 days after vaccination or missing. An AE with missing time of onset will be considered to have occurred just after the vaccination indicated by the visit number, so will be included in these tables.

Note: Unsolicited non-serious AEs that occurred before vaccination (negative time of onset) or with a time of onset higher than defined above will not be included in analysis, but will be listed separately.

Duration

Duration is derived from the start and stop dates of the unsolicited non-serious AE provided in the clinical database:

stop date of unsolicited non-serious AE – start date of unsolicited non-serious AE + 1.

The duration should be considered as missing only if one or both of the start and stop dates of the unsolicited non-serious AE is missing or partially missing.

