5.4.2.3 SAEs

Last vaccination

The last vaccination before any SAE is defined as the study vaccination at Visit 1.

Time of onset

Time of onset will be computed using the same methodology than for unsolicited non-serious AEs described in [Section 5.4.2.2](#).

SAEs will be analyzed throughout the study using the following periods:

- During the study (i.e., all SAEs occurred during the study)
- Within 30 days after vaccination

An SAE with missing time of onset will be considered to have occurred just after the vaccination indicated by the visit number, so will be included in these tables.

Note: SAEs that occurred before vaccination (negative time of onset) will not be included in analysis, but will be listed separately.

Duration

Duration will be computed using the same methodology than for unsolicited non-serious AEs described in [Section 5.4.2.2](#).

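### A month-only AE start date is handled as fully unknown, so an event that must lie outside Days 0-30 is still tabulated as within 30 days

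*SAP*

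**What the plan says.** SAP 5.4.2.2 computes time of onset for an unsolicited non-serious AE as start date minus vaccination date. It adds: "The time of onset should be considered as missing only if one or both of the dates are missing or partially missing". The 30-day period is then defined as "AEs with a time of onset between 0 and 30 days after vaccination or missing". For placement it says: "An AE with missing time of onset will be considered to have occurred just after the vaccination indicated by the visit number". There is only one vaccination to choose from: "Last vaccination before any unsolicited non-serious AE is the study vaccination at Visit 1".

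SAP 5.4.4.1 repeats the rule ("If the start date is missing or partially missing, the time of onset will be considered to be missing") and closes off any use of the known part of the date: "Missing or partially missing start dates for unsolicited AEs will remain missing and not be imputed". It keeps such events in the analysis according to the visit at which they were collected.

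A note in SAP 5.4.2.2 removes events with a negative onset, or an onset beyond the period, from the analysis and lists them separately. For SAEs, SAP 5.4.2.3 states: "Time of onset will be computed using the same methodology than for unsolicited non-serious AEs". Its own note removes only SAEs with a negative onset. SAEs are tabulated both within 30 days and over the whole study.

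**The concern.** The exclusion note needs a computed onset, and a partial date never yields one. A date with month and year but no day is therefore handled as though nothing were known, even when the recorded month settles whether the event falls in the period. Two records of the same event are treated in opposite ways: the more precise one is excluded and the less precise one is counted.

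At stake is whether the 30-day rows for unsolicited AEs, adverse reactions and SAEs contain only events that could have started in that period. Nothing inferential depends on them. SAP 4.7 calls the safety analysis descriptive, with no testing.

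**Working it through.** The documents give no figure on this point, so there is none to reproduce. The check traces the rule and then counts when it can give a wrong entry.

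**Inputs**
- Unsolicited AEs are collected from Day 0 to Visit 2, Day 30 (+14 days): Protocol 5.1.1.
- Planned vaccination period, 22 May to 11 November 2020: Protocol 5.1.5. This is 10 + 30 + 31 + 31 + 30 + 31 + 11 = 174 dates.
- Planned arm size, 180: Protocol 12.5 and SAP 2.

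**Step 1: one event, two records.** Take a vaccination on 31 August 2020. Day 30 is 30 September, Day 31 is 1 October and Day 44 is 14 October.

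| Recorded start | Onset under the SAP | Result |
|---|---|---|
| 1 October 2020 | Day 31 | Excluded, listed separately |
| October 2020, day unknown | Missing | Counted within 30 days |

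No October date is within 30 days of 31 August, so the second entry is wrong on the recorded data. Likewise, for vaccination on 22 May 2020, Day 30 is 21 June and Day 44 is 5 July. A start of July 2020 cannot be earlier than Day 40, yet it is counted.

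**Step 2: when this is possible.** A month-only date lies wholly after Day 30, and can still be collected, when the first of that month falls between Day 31 and the day of Visit 2. If Visit 2 is on Day V, each month boundary makes V - 30 vaccination dates eligible, namely those 31 to V days before the first of the month. Six boundaries apply, 1 July to 1 December 2020.

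| Visit 2 day for all subjects (assumed) | Eligible vaccination dates | Share of 174 |
|---|---|---|
| 30 | 0 | 0% |
| 35 | 6 × 5 = 30 | 17% |
| 40 | 6 × 10 = 60 | 34% |
| 44 | 10 + 5 × 14 = 80 | 46% |

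In the last row the 1 July boundary gives 10 dates rather than 14, because vaccination starts on 22 May.

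**Step 3: share of onset days.** The counts above are of vaccination dates, not events. With every subject followed to Day 44, about 25% of the Day 31-44 onset days are affected. Over Days 0-44 that is 0.2545 × 14/45 = 7.9%, about 8%. It must still be multiplied by the fraction of AEs with month-only dates, which the documents do not give.

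**Step 4: effect on a table row.** One subject in an arm of 180 is 1/180 = 0.56 percentage points. For an assumed 1 to 5 subjects in one row the shift is 0.6 to 2.8 points. A subject already counted in that row for another event adds nothing to the percentage.

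**Step 5: SAEs.** An SAE after Day 30 belongs in the whole-study table in any case, so only the shorter-period rows can be wrong. SAP 4.7.2 (Table 6, footnote) also has a 7-day SAE row. SAP 5.4.2.3 does not say clearly whether an SAE placed just after vaccination enters it. For vaccination on 10 June and an SAE dated July 2020, the earliest possible onset is Day 21, so a 7-day entry would be wrong.

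**The case against.** The convention is deliberate and consistent. SAP 5.4.2.2 names missing onset as part of the 30-day definition, SAP 5.4.4.1 repeats it, and the rule counts uncertain events in rather than out, equally in both groups. That is a sound default when timing is unknown. It does not justify counting an event whose recorded month rules out the period.

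Events on Days 31-44 are still valid study AEs: the safety endpoint in Protocol 9.2.2.2 runs up to Visit 2. This stands. The departure is from the SAP's narrower 30-day label, not from the protocol endpoint.

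Partial dates should be few. Diary cards are reviewed at Visit 2, sites clarify missing diary data (Protocol 13.2), queries are completed before database lock (13.4.1) and a blind data review precedes lock (11.3). This also stands and keeps the point small.

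A reader might infer that the tables will hold pre-vaccination events reported as vaccine reactions, since SAP 5.4.4.1 treats missing causality as related. The documents do not support that as a realistic outcome. Unsolicited AE collection starts at Visit 1, pre-existing conditions are not AEs unless they worsen (Protocol 9.2.2.1), and the investigator is told to class an event that began before vaccination as not related (9.2.2.3.4). The SAP's notes on negative onset show that stray records are foreseen, so the gap exists, but it is mainly theoretical.

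A reader might also take 46% as the share of subjects or events affected. It is neither. It is a ceiling on vaccination dates that requires every Visit 2 on Day 44.

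**Conclusion.** The point holds as a small error in the written rule. For identifiable records, the SAP tabulates as within 30 days an event that its own exclusion note would remove if the date were complete, and no other section corrects this. The opportunity ranges from none (every Visit 2 on Day 30) to 80 of 174 planned vaccination dates (every Visit 2 on Day 44). Vaccinations are assumed to fall within the planned calendar. The number of month-only dates is unknown and assumed small. Each affected subject moves a whole-arm row by at most 0.56 points, taking 180 subjects per arm. The age-group and sex rows of the safety overview have smaller denominators, so one subject moves them more; the documents do not give those sizes.

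The effect is confined to descriptive safety tables. It does not touch the seroresponse comparison and gives no reason to expect bias between groups.

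**What to change.** In SAP 5.4.2.2, 5.4.2.3 and 5.4.4.1, replace the treatment of partial start dates with a rule based on the earliest and latest dates that the known month and year allow:

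- Count the event as within 30 days only if that range overlaps Days 0-30.
- If the whole range precedes vaccination, list the event separately, as both sections already do for a negative onset.
- If the whole range is after Day 30, list a non-serious AE separately, as SAP 5.4.2.2 already does for full dates, and keep an SAE in the whole-study table only.
- Keep the present inclusive rule for fully missing dates.

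State also whether an SAE with missing or partial onset enters the 7-day row.

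The cost is a sentence or two in the SAP and a short derivation. It needs no new data, and the cautious default for unknown dates is kept.
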